#### STUDY PROTOCOL

**RECEDE study (Reducing Colonoscopies in those without bowEl DiseasE)** 

#### **1** SUMMARY OF RESEARCH

#### 1.1 Lay Summary

Investigating people with bowel symptoms uses a test that detects traces of blood in the stools, the FIT test. There are many possible reasons for positive tests. A few people have cancer. However, most participants with symptoms don't have any serious bowel disease but have benign problems such as piles or irritable bowel syndrome (IBS). It is very difficult to diagnose on symptoms alone, those participants who have serious bowel disease and those who do not.

After a positive test, people are invited for colonoscopy– a sort of articulated tube that is passed up the bowel, or a computed tomography colonography (CTC) – a radiological technique used to image the large bowel. Most people invited for colonoscopy or CTC don't have cancer. Only about 5% of those with positive FIT tests have cancer. About 25% have other serious bowel diseases (pre-cancerous polyps or inflammatory bowel disease), but most have nothing serious wrong at all. So they have the inconvenience and discomfort of having a CTC or colonoscopy but don't get any benefit from it.

We want to try adding another test, the volatile organic compound (VOC) test, to see if we can separate those with positive FIT tests who do have something serious, from those who don't. The VOC test uses a urine sample. Using both tests might also be better for detecting cancer and other serious bowel diseases. FIT alone misses about 20%.

So we think that using both tests might not only be better for detecting cancer, but also might mean that a lot of people will avoid having to have an invasive colonoscopy or CTC.

We will recruit 1,915 participants with bowel symptoms from NHS trusts in the UK. They will provide stool samples for FIT and urine for VOC analysis. They will have colonoscopy or CTC to get a definite diagnosis. Then we will look at their FIT and VOC test results to see if in future, people with both tests negative don't need invasive colon investigations.

#### 1.2 Scientific Abstract

*Research Question*: Can the addition of urine VOC to stool FIT testing rule out significant bowel disease (SBD) and by so doing, reduce unnecessary invasive tests (colonoscopy/CTC) – the right test for the right participant?

*Background:* There is currently disparity between demand and available resources for colonoscopy. At present around 300,000 participants (and rising) are being referred annually to NHS trusts suspected of colorectal cancer (CRC) (1). These participants are offered invasive colonic examinations (colonoscopy or CT colonography) but only 30% will have significant bowel disease (2). Significant bowel disease (SBD) includes neoplasia (cancer and benign tumours) and significant treatable benign conditions such as inflammatory bowel disease (3). Of the remaining 70%, 40% have completely normal colonic investigations (2) and 30% have functional bowel conditions such as irritable bowel syndrome or diverticular disease.

Set against this there is and will remain for the foreseeable future a capacity shortfall for colonoscopy and CTC. This limits the ability of the NHS to extend colorectal cancer detection within the Bowel Cancer Screening Programme (BCSP) or to target those participants that present for the first time through the Emergency Department (25% of all colorectal cancer diagnoses).

The increasing demand, limited capacity and lack of a triage tests have left NHS trusts with a conundrum of how best to stratify those with symptoms and at risk of SBD including CRC. The National Institute for Health and Care Excellence (NICE) has recommended a stool test (faecal immunochemical testing for haemoglobin, known as FIT) in the assessment of those suspected of CRC (4). NICE have recommended 10  $\mu$ gHb/g faeces as the cut off for investigation of people with low risk symptoms who, account for only 10% of those referred with suspected CRC. When applied to high risk symptom groups, FIT will *miss* a significant number of participants with CRC (~10%) if used on its own at the threshold recommended by NICE (10  $\mu$ gHb/g faeces). FIT will also *miss* a large number of significant potentially pre-cancerous polyps (~40%) (6, 7). Early detection and removal of such polyps will reduce risk of CRC (8).

The Bowel Cancer Screening Programme (BCSP) has set a FIT cut off of >120  $\mu$ gHb/g faeces (9, 10), compared to the NICE threshold of 10  $\mu$ gHb/g faeces, but even at the lower threshold recommended by NICE some SBDs will be missed (2, 7, 11, 12). Whilst a lower threshold might improve detection of SBD, it will increase the number of colonoscopies and CTCs that find no abnormality. Consequently, we have been investigating a urine test (in addition to FIT) to improve detection of participants with SBD with a view to reducing unnecessary colonoscopies and CTCs. The urine test analyses volatile organic compounds (VOCs) that originate from the body and provides a chemical 'fingerprint' that is disease specific. Stool FIT and urine VOCs identify different biological characteristics of SBD – haemoglobin (as a marker of excess blood loss) versus metabolic response to inflammation. In a preliminary study of 562 participants, stool FIT on its own (at a threshold determined from the data) detected 80% of those with colorectal cancer. However, the addition of urine chemical testing improved this to 97% (6). The number of CRC cases missed by combined FIT and urine chemical testing is similar to that of colonoscopy, the current gold standard.

### *Aim:* To investigate the diagnostic accuracy of stool FIT plus urine VOC compared to stool FIT alone to improve detection of SBD.

This may enable reduction in number of colonoscopies and CTCs in those without SBD.

#### Methods, study population and design

RECEDE study will be a multicentre diagnostic accuracy study involving secondary care centres, recruiting 1,915 participants referred for colonic investigations.

The study will compare single index testing with FIT with dual testing with FIT plus VOC. The reference standard will be colonoscopy (complete examination) or CTC.

#### Primary outcome

Primary outcome will be diagnostic accuracy for sensitivity, specificity, NPV and PPV of stool FIT plus urine VOC compared to stool FIT alone in the detection of SBD.

#### Secondary outcome

Secondary outcome measures will include:

- I. ROC curve of stool FIT plus urine VOC in detection of SBD.
- II. The potential number of colonoscopies and CTCs avoided in those without SBD,
- III. Total NHS & Personal Social Services (PSS) costs, and
- IV. Total quality-adjusted life years (QALYs) associated with each option.

Exploratory outcome measures will include:

Calculation of the number of CTC negative participants who later present with SBD or microscopic colitis

IRAS 282247\_RECEDE protocol\_v2.2\_11.02.2022 Page **13** of **50** 

 Sensitivity, specificity, NPV and PPV of stool FIT plus urine VOC in the detection of SBD + microscopic colitis

#### 1.3 Knowledge gap this research will address

RECEDE study will address the following knowledge gaps:

- I. Whilst FIT is valuable for CRC detection, it will still miss some SBD at the cut offs recommended. Hence, we need to understand whether urine VOC added to FIT can improve detection of SBD such that those without SBD can avoid a colonoscopy or CTC.
- II. With implementation of non-invasive triage testing, what are the cost savings to the NHS?

#### 1.4 Proposed study

RECEDE study will be a multicentre prospective diagnostic accuracy study involving secondary care centres to recruit 1,915 participants referred for colonic investigations.

#### 1.5 Study population

All participants referred from primary care with lower gastrointestinal symptoms either routinely or urgently in accordance with NICE NG12 criteria. Sites will include NHS Trusts where colonoscopy or CTC is offered.

#### 1.6 Impact of COVID-19 on Patient pathways

COVID-19 has brought about a change in the way people who are experiencing lower GI symptoms are referred into secondary care (illustrated in Appendix C Figure 3). Previously, FIT testing would be used in some regions, and only on low risk patients (~10% of all patients) before they were referred to secondary care. They would then be referred for colonoscopy only if the FIT test was positive. However, in most regions and patients, a person presenting to their GP with GI symptoms would be referred either routinely or urgently in accordance with the NICE guidelines (4) without the need for a prior FIT test.

Since the outbreak of COVID-19 within the UK, hospitals have seen a drastic fall in the number of patients being referred with GI symptoms. However since lockdown measures have eased and at time of writing this protocol, we are now beginning to see a rise in the number of referrals, and there is a backlog to be cleared. To manage limited colonoscopy capacity due to the impact of COVID-19 and colonoscopy (which is a potential aerosol generating procedure), FIT may be used (outwith) NICE guidance to triage referrals to colonoscopy.

In addition there has also been a stark increase in the number of patients being referred for a CT scan instead of colonoscopy. Our preliminary data shows that over 25% of all GI referrals to secondary are currently having CT scans. CT scan is a radiological procedure that was often favoured for older patients with comorbidities as they are more at risk of adverse events during a colonoscopy. However, COVID-19 has caused a shift in practice, whereby more people are now being referred for CT scans, and this shift appears to be here to stay for the long term. CT scans are split into regular CTs and CTC, the latter of which has been shown to have similar sensitivity to colonoscopy for the detection of colorectal cancer (Halligan et al., 2005) and large polyps (Pickhardt et al., 2003). It is common for CTC positive patients to then have a colonoscopy to receive histological confirmation of any diagnosis. Some NHS Trusts have already adopted CT scans for 100% of referrals, using colonoscopy as only a confirmatory diagnostic follow up.

NHS England has suggested that FIT may be used in secondary care to triage timing of colonoscopy or CTC rather than need for colonoscopy or CTC, or to discharge patients if FIT is returned negative. This is because there is recognition of the lack of evidence to guide referral for colonoscopy or CTC. This is the very reason for undertaking the RECEDE study. NHS England guidance also actively encourages primary care physicians to continue to refer to secondary care all those with lower GI symptoms and not to delay or defer such referrals.

In summary, it is likely there will be a population (unable to estimate proportion at this time) that will have had a FIT test prior to their colonoscopy or CTC. The time interval from FIT test to colon investigation will be highly variable hence for participants into RECEDE, we will still re-test FIT alongside urine VOC as originally planned if the participant has a wait of over 4 weeks between their first FIT test and their colonoscopy or CTC. If their colon investigation is scheduled within 4 weeks of the first FIT test (i.e. for urgent referrals) then we will be able to use the first test alongside VOC analysis for the primary outcome analysis and not need to request a second test. The initial FIT test will be purely to triage *timing* of colonoscopy or CTC rather than *need* for colonoscopy or CTC. Due to limited capacity, initial recruitment rate will be slower, possibly only half the rate of what was previously predicted for the next 12 months but the aims of RECEDE are still achievable.

FIT kits are fairly uniform across practices - both HMJac-K and OC-Sensor are most commonly used, however these kits collect different quantities of faecal matter into different buffer volumes and so cannot be directly compared. However a conversion factor is available in order to equalise the tests (71). Therefore if a recruiting site uses a FIT test other than the HMJac-k to triage their patients we are able to accurately compare the two.

Further, as the waiting list for secondary care appointments continues to grow we are seeing an increase in the number of primary care lower GI referrals sent directly to A&E. These patients are then referred for colonoscopy or CTC from here. These patients are eligible for RECEDE however currently their medical history does not become available on the hospital system making them difficult to recruit. If this happens, once a patient consents into the study we will approach their GP to request the participant's medical history be sent to the study team. The current consent form already requests permission to access the patients' health records.

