#### SCHEDULE OF EVENTS

**Table 1** Schedule of events for collection of stool FIT and urine VOC for both face-to-face and remote
 recruitment scenarios.

Face to Face:

Observation	Baseline (referral visit)	Day of colonoscopy or CTC (before procedure)	24hrs & 72hrs post colonoscopy or CTC	3 weeks post colonoscopy or CTC	Analysis complete and results available
Eligibility screening					
	Х				
Informed consent	Х				
Baseline data	Х				
Urine sample for VOC analysis	Xª				
Stool sample for FIT test	Xp				
Participant questionnaires: EQ-5D*	Xc	х	Xc	Xc	
Resource use questionnaire*		х		Xc	
Colonoscopy or CTC					
results and adverse				Х	
outcomes					
Follow Up in CTC					Х
negative patients					

Remote:

Observation	Baseline (remotely)	Pre- colonoscopy or CTC (participant at home)	Day of colonoscopy or CTC (before procedure)	24hrs and 72hrs post colonoscopy or CTC	3 weeks post colonoscopy or CTC	Analysis complete and results available
Eligibility screening	х					
Informed consent	X (via telephone)					
Baseline data	Х					
Urine sample for VOC analysis (kit to be posted to participant)		Xď				
Stool sample for FIT test (kit to be posted to participant)		Xp				

Participant	VC	V	M	XC	
questionnaires:	Xc	Х	Xc	Xc	
EQ-5D*					
Resource use		V		VC	
questionnaire*		Х		Xc	
Colonoscopy or					
CTC results and				х	
adverse				^	
outcomes					
Follow Up in CTC					Х
negative patients					

Note - all sample collections are designed to be timed, if possible, with participant's attendance to clinic or treatment to minimise additional visits. If this is not feasible, there is a postal option or delivery to local GP for transport to central site only\*

- (a) If participant is unable to provide a urine sample at Baseline, they can return sample to their GP surgery\* or drop it off at the hospital. If this is not possible, participants also have the option to collect a urine sample, 24 hours prior to bowel prep, and bring it with them on the day of colonoscopy/CTC (participant will have to keep the sample in the freezer and, if required, place in a provided cool bag when bringing back to the hospital if sample is likely to be out the freezer for over 1 hour)
- (b) Only provide participant with FIT testing kit and pre-paid envelope for stool sample collection at home if it will be 4 weeks between their first referral FIT test and their colonoscopy/CTC appointment.

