#### 5 ELIGIBILITY CRITERIA

5.1 Inclusion criteria

- All participants referred either routinely with lower gastrointestinal symptoms or urgently (fulfilling the national criteria for referral NICE NG12) for colonoscopy or CTC that is determined by their overseeing clinician
- Minimum age of 18
- Able to provide informed consent
- Have the ability to return both stool and urine samples

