#### 7.3 Stool FIT

Samples with traces of haemoglobin in the faeces at and above the cut off value  $10\mu$ gHb/g are defined as suspected SBD. Any previous FIT results collected to triage patients can be sourced from patient records.

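### Which FIT is analysed depends on the wait, and the wait depends partly on the first FIT result, so FIT-alone sensitivity is expected to be biased upward by an unknown amount

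*Protocol*

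**What the plan says.** Section 1.6 of the Protocol expects some participants to arrive with a FIT already done, in a share it cannot give: "it is likely there will be a population (unable to estimate proportion at this time) that will have had a FIT test prior". For them it fixes which result is used.

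- Long wait: "we will still re-test FIT alongside urine VOC as originally planned if the participant has a wait of over 4 weeks" between the first FIT and the procedure.
- Short wait, which the section equates with urgent referral: for a procedure inside that limit, "we will be able to use the first test alongside VOC analysis for the primary outcome analysis and not need to request a second test".
- Role of the first test: "The initial FIT test will be purely to triage" the timing of colonoscopy or CTC, as opposed to the need for it.

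Footnote (b) to Table 1 in the Schedule of Events turns this into a kit instruction: a stool kit is issued only "if it will be 4 weeks between their first referral FIT test and their colonoscopy/CTC appointment". Section 7.3 makes retrieval of the earlier result optional: "Any previous FIT results collected to triage patients can be sourced from patient records". Under Section 8.2.2 a case is positive on the dual test if either FIT or VOC is positive, FIT-only accuracy is also reported, and anyone missing an index test is excluded. Section 8.3 compares FIT + VOC with FIT and takes its accuracy inputs from this study.

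**The concern.** Put together, the statements in Section 1.6 form a chain. The first FIT result influences the wait, and the wait decides whether the first or a second FIT is analysed. Selection of the index-test result is thus linked to that result. If triage works as intended, a person with a positive first FIT is seen sooner and tends to keep that result, while a person with a negative one waits longer and tends to get a second chance to be positive.

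FIT alone is the comparator in the study aim, the primary outcome statement and the economic evaluation. If its sensitivity is overstated, a service that tests once would miss more SBD than reported. The pool of FIT-negative SBD in which VOC can add anything would also look smaller than it is.

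Footnote (b) adds a separate defect that needs no assumption. Taken literally, it gives no kit to someone with no earlier FIT, whereas the study flow chart and Section 6 ask every participant for a stool sample. It also says 4 weeks where Section 1.6 says over 4 weeks.

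**Working it through.** **Plan's own figures.** Section 8.1: 200 SBD cases / 0.19 prevalence = 1052.6, so 1053; 1053 / 0.55 returning both samples = 1914.5, so 1915. This reproduces, and the present point does not change it.

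**Inputs from the protocol**
- Sensitivity of one FIT for SBD: s = 1 - 0.37 = 0.63 (Section 1.9, Dual Testing: 37% of those with SBD are FIT negative).
- SBD cases: 200 (Section 8.1).
- FIT specificity: 0.86 (Section 1.9) and 0.93 (Appendix D). Both are for cancer and serve only as stand-ins for SBD.

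**Inputs assumed, because the protocol gives none**
- π, share with a prior FIT: 0.25 to 1.
- r, chance that a second FIT is positive given a negative first FIT in SBD: 0.2 in the middle case.
- q₋ and q₊, chance of waiting over 4 weeks after a negative and a positive first FIT: 0.8 and 0.2.
- The re-test replaces the first result (the natural reading, though not stated), and both tests have the same marginal sensitivity.

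**Formula.** Let d = (1 - s)r be the probability of negative then positive. With equal marginals, positive then negative also has probability d. For someone with a prior FIT, the analysed FIT is positive with probability

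s(1 - q₊) + q₊(s - d) + q₋d = s + d(q₋ - q₊).

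Over all SBD cases: Se(FIT analysed) = s + π·d·(q₋ - q₊).

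**Middle case.** d = 0.37 × 0.2 = 0.074 and q₋ - q₊ = 0.6.

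| π | Bias | FIT-alone sensitivity | Extra positives per 200 SBD |
|---|---|---|---|
| 0.25 | 0.25 × 0.074 × 0.6 = 0.011 | 0.641 | 2.2 |
| 0.50 | 0.022 | 0.652 | 4.4 |
| 1.00 | 0.044 | 0.674 | 8.9 |

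A simulation of 2,000,000 cases at π = 1 returned 0.6744, against 0.6744 from the formula.

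**Limits.** If r = 0 or q₋ = q₊, the bias is 0. The extreme (π = 1, every negative and no positive re-tested, repeat tests independent so r = 0.63) gives 0.63 + 0.37 × 0.63 = 0.863.

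**Effect on FIT + VOC.** Suppose a single FIT with VOC reaches the planned 0.97. Then VOC detects 1 - 0.03/0.37 = 0.919 of FIT-negative SBD, and the gain is 0.97 - 0.63 = 0.34. Hold 0.919 fixed and let FIT be 0.674: the combined sensitivity is 1 - 0.326 × 0.081 = 0.974 and the gain is 0.299.

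**Specificity.** With an assumed 5% conversion in people without SBD, the same waits and π = 1: 0.93 - 0.93 × 0.05 × 0.6 = 0.902, and 0.86 - 0.86 × 0.05 × 0.6 = 0.834. At π = 0.25 the fall is a quarter of that, about 0.7 points.

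**The case against.** The trigger is the wait, never the FIT result. Urgency is also set by referral criteria: Section 5.1 admits "All participants referred either routinely with lower gastrointestinal symptoms or urgently (fulfilling the national criteria for referral NICE NG12"), so a FIT-negative person who is urgent on symptoms keeps the first result. A FIT-positive person caught in the backlog that Section 1.6 describes is re-tested. Both offset the bias, and participants without a prior FIT are untouched. The rule also has a sound purpose, since it limits the interval between index test and reference standard. The same FIT enters both strategies, so the dual-test sensitivity on which the study is sized hardly moves, and the error in the VOC gain runs against the study's hypothesis. With 200 cases the 95% half-width around 0.63 is about 0.067 (1.96 × √(0.63 × 0.37/200)), larger than any middle-case bias.

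All of this stands, and it rules out stronger readings. A reader might infer that positives always keep their first result and negatives always get a second, so that the analysed FIT amounts to positive on either test. The documents do not support that. With r = 0.2, the full either-test value would be 0.63 + 0.074 = 0.704, while the middle case at π = 1 is 0.674. A reader might also infer that FIT-alone sensitivity is definitely inflated. That needs both unequal waits and discordant repeats, and the protocol quantifies neither.

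The direction remains. The bias would reverse only if positives waited longer than negatives, which would defeat triage of timing. That it runs against the hypothesis does not make it harmless, because it flatters a single FIT as a rule-out test. A sensitivity analysis can be left to the SAP, but optional capture of the first result cannot be repaired there.

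**Conclusion.** The concern holds as a conditional bias. As Section 1.6 and footnote (b) are written, selection of the analysed FIT is linked to the first FIT result among participants with a prior FIT. FIT-alone sensitivity is expected to be too high, specificity too low and the added value of VOC understated.

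The size is unknown. Under the assumed middle case, sensitivity rises from 0.63 to about 0.64-0.67. At the top of that range the VOC gain falls from 0.34 to about 0.30, while the combined sensitivity moves only from 0.970 to 0.974. The bias vanishes if waits do not differ by result or repeat tests agree. It does not threaten the sample size or the dual-test sensitivity, but it does affect the comparator and the economic inputs.

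The wording of footnote (b) needs correction whatever the size of the bias.

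**What to change.** 1. **Capture.** In Section 7.3, change the optional retrieval of earlier FIT results to a requirement wherever they are available, and record every FIT result per participant with its date and kit. The kit matters because Section 1.6 allows different triage kits linked by a conversion factor.
2. **Analysis.** Keep the 4-week rule for the primary tables. Add a sensitivity analysis of the FIT-alone and FIT + VOC 2x2 tables, and of the economic model inputs, using the first FIT for everyone who has one. Report the proportion re-tested by first FIT result.
3. **Wording.** Reword footnote (b) so that participants with no prior FIT receive a kit, and align its 4 weeks with the over 4 weeks of Section 1.6.

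**Cost.** One extra set of tables, some record retrieval and a wording amendment. First-FIT data will be incomplete for patients referred through A&E, whose history Section 1.6 says is not on the hospital system.

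**Alternatives not recommended as primary.** Using the first FIT for all would restore the older results that the rule is meant to remove. A study kit for all as the only primary FIT would break the link to the first result, at £18 per test. But it would make inclusion depend on kit return, with about 55% expected to return both usable samples (Section 8.1) and missing index tests excluded (Section 8.2.2).
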